4.3.2.1.2 Dose Adjustments in Case of Red Blood Cell Transfusion

In case of an RBC transfusion due to worsening anemia secondary to inadequate doses or to poor response to Mircera, the dose (administered at the next scheduled dosing day, if possible) should be adjusted according to the guidelines in [Table 3](#).

In case of an RBC transfusion to replace acute blood loss, the dose should not be changed, and the next dose should be administered as scheduled.

4.3.3 Investigational Medicinal Product Accountability

All IMPs (Mircera) required for completion of this study will be provided by the Sponsor where required by local health authority regulations. The study site will acknowledge receipt of IMPs supplied by the Sponsor, using the IxRS to confirm the shipment condition and content. Any damaged shipments will be replaced.

IMPs will either be disposed of at the study site according to the study site's institutional standard operating procedure or be returned to the Sponsor (if supplied by the Sponsor) with the appropriate documentation. The site's method of destroying Sponsor-supplied IMPs must be agreed to by the Sponsor. The site must obtain written authorization from the Sponsor before any Sponsor-supplied IMP is destroyed, and IMP destruction must be documented on the appropriate form.

Accurate records of all IMPs received at, dispensed from, returned to, and disposed of by the study site should be recorded on the Drug Inventory Log.

4.3.4 Continued Access to Mircera

Currently, the Sponsor does not have any plans to provide the Roche IMP (Mircera) or any other study treatments or interventions to patients who have completed the study. The Roche Global Policy on Continued Access to Investigational Medicinal Product is available at the following website:

http://www.roche.com/policy_continued_access_to_investigational_medicines.pdf

4.4 CONCOMITANT THERAPY

Concomitant therapy consists of any medication (e.g., prescription drugs, over-the-counter drugs, vaccines, herbal or homeopathic remedies, nutritional supplements) used by a patient in addition to protocol-mandated treatment within 3 months before screening. All such medications should be reported to the investigator and recorded on the Concomitant Medications eCRF.

4.4.1 Permitted Therapy

All treatments (medications and medical procedures) are permitted before screening, during the screening period, and throughout the 20-week treatment period, except for those listed in Section [4.4.5](#).

4.4.2 Iron Supplementation

An adequate iron status is a prerequisite to achieve and maintain target Hb levels. Iron deficiency during treatment may cause a reduced erythropoietic response to epoetin therapy. In addition, epoetin therapy results in increased erythropoiesis that may lead to a depletion of iron stores. The iron status will be monitored throughout the study by assessing serum ferritin and TSAT. TSAT will be calculated as described in [Appendix 3](#). The percentage of hypochromic red cells can be determined instead of TSAT.

Adequate iron status is defined as follows:

Serum ferritin \geq 100 ng/mL

or

TSAT \geq 20% (or percentage of hypochromic red cells $<$ 10%)

Patients must be iron-replete at baseline to be enrolled in this study and should maintain an adequate iron status throughout the treatment period. For baseline, iron status should be assessed using the mean of two values measured during screening (Weeks -3 and -1).

Supplemental iron will be administered to prevent iron deficiency during the screening period and during the study, and to maintain adequate iron status. Therefore, oral or IV iron will be given during the entire study period (screening, dose titration, and evaluation periods) according to center practice. If iron treatment is ongoing at the start of the study, it should not be interrupted.

To avoid iron toxicity, caution is suggested in patients with serum ferritin $>$ 500 ng/mL or TSAT $>$ 30%.

All oral and IV iron supplementations administered within 3 months before screening and started/stopped at any time during the screening and treatment periods should be documented in the iron supplementation section of the eCRF.

Iron Loading

In case of inadequate iron stores at the end of screening, the patient should receive iron loading according to center practice. After completion of the iron loading, the patient will be allowed to be re-screened. New assessment of iron stores should be performed at least 1 week after iron loading.

4.4.3 Red Blood Cell Transfusions

RBC transfusions may be given during the treatment period in case of medical need, that is, in severely anemic patients with recognized symptoms or signs of anemia (e.g., in patients with acute blood loss or in patients whose Hb has declined to critical levels). Every reasonable effort should be made to avoid RBC transfusions in patients with Hb concentrations above 8 g/dL.

All RBC transfusions administered during the study should be documented (i.e., specified by type, number of units transfused, and total volume transfused) in the RBC transfusions section of the eCRF. The pre-transfusion Hb level must be measured before each RBC transfusion and recorded on the appropriate page in the eCRF.

The indication for the RBC transfusions (e.g., the etiology of the acute blood loss or worsening of anemia if no other etiology is known) should be recorded as an adverse event on the eCRF page and the RBC transfusions listed as treatment on the same eCRF page.

4.4.4 Dialysis

Dialysis modality at study start (HD, PD, or none), number of HD sessions per week, the type of vascular access for HD, PD type, time since first dialysis, and dialysis adequacy assessments should be documented in the dialysis section of the eCRF.

In the event that a patient not previously on dialysis requires emergent or long-term dialysis treatment due to worsening of renal function, the patient should be kept in the study, whenever possible, until the final visit. The route of administration for Mircera should stay the same (SC). The start of dialysis and dialysis modality should be documented in the dialysis page of the eCRF.

Dialysis modality changes (i.e., switch from PD to HD) may be performed during the treatment period in case of medical need. If a switch from PD to HD during the study becomes necessary, the patient can continue to participate in the study as long as the SC route of administration is maintained. The visits should occur on the day of the mid-week dialysis. The change of dialysis should be documented in the dialysis page of the eCRF.

4.4.5 Prohibited Therapy

Use of the following concomitant therapies is prohibited as described below:

- *Other* IMPs (defined as any material [i.e., placebo or drug] dispensed under the provision of a protocol) within 4 weeks before screening, during screening, or during the treatment periods.

Participation in studies testing investigational devices or dialysis solutions should be reported to the Sponsor in advance and approved by the Sponsor.

- Non-Food and Drug Administration (FDA) or European Medicines Agency-approved biosimilar ESAs within 12 weeks before screening or during screening
- RBC transfusions within 8 weeks before screening or during screening (see also Section [4.4.3](#))
- Immunosuppressive therapies known to exacerbate anemia, such as cyclophosphamide, sirolimus, tacrolimus, azathioprine, and mycophenolate mofetil, administered the last 12 weeks before the first screening visit

- Whenever possible, intermittent treatment (i.e., start or stop) or dose change of medications known to influence Hb concentration should be avoided.

These medications include androgens (known to improve anemia), angiotensin-converting enzyme inhibitors, angiotensin II receptor blockers, and immunosuppressive therapies, except for corticosteroids for a chronic condition, cyclosporine, and monoclonal /polyclonal antibodies

If drugs that are highly bound to RBCs (e.g., cyclosporine) are given during the study, blood levels of these drugs should be monitored and their dosage adjusted as the Hb rises.

4.5 STUDY ASSESSMENTS

The schedules of activities to be performed during the study are provided in [Appendix 1](#) and [Appendix 2](#). All activities must be performed and documented for each patient.

Patients will be closely monitored for safety and tolerability throughout the study. Patients should be assessed for toxicity prior to each dose; dosing will occur only if the clinical assessment and local laboratory test values are acceptable.

Throughout the screening period and the 20-week treatment period (dose titration and evaluation periods), the study visits should be scheduled, *if possible*, on the same day of the week. For patients undergoing HD or patients converting to HD, the visits should occur on the day of the mid-week dialysis.

A follow-up visit will be performed for all patients at study end (Week 21) or at any time during the study in case of premature withdrawal. In case of premature withdrawal due to kidney transplantation, the follow-up visit must take place before the transplantation; otherwise, there will be no follow-up visit.

Patients completing the 20 weeks of treatment with Hb within ± 1 g/dL of their baseline Hb and within the target range of 10–12 g/dL will be eligible to enter an optional 24-week safety extension period.

4.5.1 Informed Consent Forms and Screening Log

Written informed consent from the parent/legal guardian and willingness of the parent/legal guardian to abide by the requirements of the study, and written informed consent or assent from the child where appropriate, must be obtained before performing any study-related procedures (including screening evaluations). If required by national legislation, patients < 18 years of age at screening who are legally considered to be adults according to national legislation must consent in their own right.

Informed Consent Forms for enrolled patients and for patients who are not subsequently enrolled will be maintained at the study site.

Eligibility will be assessed during an initial screening period. All screening evaluations must be completed and reviewed to confirm that patients meet all eligibility criteria before enrollment. The investigator will maintain a screening log to record details of all patients screened and to confirm eligibility or record reasons for screening failure, as applicable.

Patients who fail screening may be re-screened if it is considered likely that they could later become eligible. Patients who are not eligible will be allowed to undergo a maximum of two new rounds of screening assessments. All eligibility criteria have to be reassessed during the new screenings.

Provided that the efficacy and safety profiles for the patient are acceptable, at least 2 weeks prior to the follow-up visit (Visit 10, Week 21), the investigator should discuss with the parents/legal guardians and, if appropriate, with the patient, the possibility of continuing with an optional safety extension period. A new signature on the informed consent (and, if indicated, on the assent) should be obtained at this time. The clinical and laboratory assessments at Week 21 (Visit 10, follow-up visit) of the core study period are also used as initial assessments for the optional safety extension period.

4.5.2 Medical History, Concomitant Medication, and Demographic Data

The following information will be collected during the screening period:

- Medical history includes etiology of CKD, dialysis modality (HD,PD or none), number of HD sessions per week, the type of vascular access for HD, anticoagulant treatment during HD, PD type, date of first dialysis treatment, dialysis adequacy assessments, previous ESA treatments, and iron supplementation. It also includes risk factors and dialysis-related events, as well as clinically significant diseases.
- In addition, all medications (e.g., prescription drugs, over-the-counter drugs, vaccines, herbal or homeopathic remedies, nutritional supplements) used by the patient within 3 months prior to screening will be recorded.
- Demographic data will include age, sex, and self-reported race/ethnicity (where permissible).
- Reproductive status and smoking history will be collected.

4.5.3 Physical Examinations

A complete physical examination, performed at screening (Week -3, Visit 1), at the follow-up visit (Week 21, Visit 10), and at the final safety extension visit (Week 45), should include an evaluation of the head, eyes, ears, nose, and throat, and the cardiovascular, dermatologic, musculoskeletal, respiratory, gastrointestinal, genitourinary, and neurologic systems. Any abnormality identified should be recorded on the corresponding page of the eCRF.

4.5.4 Height and Body Weight

Height will be collected at Week 1, Visit 3, at the follow-up visit (Week 21, Visit 10), and at the final safety extension visit (Week 45). Body weight will also be recorded throughout the study (*after dialysis for patients on HD*).

4.5.5 Vital Signs

Vital signs will be measured regularly throughout the study. They include measurements of systolic and diastolic blood pressure and pulse rate while the patient is if possible in a seated position, and they will be measured before blood sampling (see [Appendix 5](#)). The blood pressure should be measured at least twice and the average of these measurements should be recorded. An appropriate-sized cuff should be used. Blood pressure should be determined before and after the dialysis session for HD patients.

4.5.6 Laboratory Assessments

For sampling procedures, storage conditions, and shipment instructions, see the laboratory manual.

Biological samples will be destroyed no later than the time of completion of the final Clinical Study Report, with the following exception:

- *Serum samples collected for PK or immunogenicity analysis may be needed for additional immunogenicity characterization and for PK or immunogenicity assay development and validation; therefore, these samples will be destroyed no later than 5 years after the final Clinical Study Report has been completed.*

When a patient withdraws from the study, samples collected prior to the date of withdrawal may still be analyzed, unless the patient specifically requests that the samples be destroyed or local laws require destruction of the samples. However, if samples have been tested prior to withdrawal, results from those tests will remain as part of the overall research data.

Data arising from sample analysis will be subject to the confidentiality standards described in Section 8.4.

4.5.6.1 Safety Assessments

Normal ranges for the study laboratory parameters should be supplied to Roche before the study starts. Blood sampling should always be performed before ESA administration and for patients on HD before the dialysis. The following laboratory assessments will be performed throughout the study at selected visits (see the schedules of activities in [Appendix 1](#) and [Appendix 2](#)) and analyzed at the study site's local laboratory:

- Hematology: Hb, RBC, absolute reticulocyte count
- Safety laboratory: leukocytes plus differential, AST, ALT, serum albumin, ALP, C-reactive protein, potassium, phosphorus, calcium, and platelets
- Serum creatinine: measured only for patients not on dialysis
eGFR will be calculated using the Bedside Schwartz formula (see [Appendix 3](#)).

- Iron parameters: serum ferritin, serum iron, and TSAT. TSAT will be calculated as described in [Appendix 3](#) with either serum transferrin or total iron-binding capacity. The percentage of hypochromic red blood cell may be determined instead of TSAT.
- Serum pregnancy test for post-pubertal female patients of childbearing potential
- Kt/V for patients on PD
 - Frequency will follow current Kidney Disease Outcomes Quality Initiative (KDOQI) guidelines (2006).
- Kt/V or URR for patients on HD
 - Frequency will follow current KDOQI guidelines (2006).

Per individual, the trial-related blood loss (including any losses in the maneuver) should not exceed 3% of the total blood volume during a period of four weeks and should not exceed 1% at any single time. The total volume of blood is estimated at 80 to 90 ml/kg body weight; 3% is 2.4 ml blood per kg body weight (DG SANTE 2008). Blood sampling to assess the different laboratory parameters should be done routinely at the site but should not exceed the recommended maximal volume of 2.4 ml per kg per four weeks.

Samples for the following laboratory tests will be sent to one or several bioanalytical laboratories for analysis:

- Serum samples will be collected to evaluate the pharmacokinetics of Mircera administered subcutaneously (see Section [4.5.6.2](#)).
- Anti-EPO and anti-Mircera antibody will be determined at Week 1, Visit 3, at Week 9 (Visit 6), and follow-up visit (Week 21, Visit 10). An additional sample will be collected at Week 45 (Visit 16) for the patients participating in the safety extension period.

For the patients participating in the optional safety extension period, laboratory assessments will be performed every 4 weeks (see the schedules of activities in [Appendix 1](#) and [Appendix 2](#)).

4.5.6.2 Pharmacokinetic Assessments

PK sampling will be performed in all patients throughout the 20-week treatment period (dose titration and evaluation periods). Serum concentrations of Mircera will be used to evaluate the pharmacokinetics and the concentration-effect relationships in all patients. The timing of all PK and hematology samples needed for this study will coincide as much as possible with regularly scheduled visits.

Samples taken at the following timepoints will be sent to one or several bioanalytical laboratories for analysis:

- Week 1 (Visit 3) before the first Mircera dose administration
- Week 3 (Visit 4)
- Week 9 (Visit 6) before the Mircera dose administration

- Week 17 (Visit 8) before the Mircera dose administration
- Week 19 (Visit 9)
- At the patient's convenience, one additional sample between 24 hours and 5 days after any one Mircera dose administration should be collected.

A minimum of one PK sample after treatment initiation is requested in patients younger than 2 years old; the sample on Week 1 can be omitted in these patients.

The exact time of PK blood sampling must be recorded on the lab requisition form and the exact time of the preceding Mircera administration must be recorded on the appropriate page in the eCRF.

PK samples must be handled according to the procedures described in a separate document.

The standard laboratory parameters should be measured locally at the study site. PK and antibody samples will be shipped to one or several bioanalytical laboratories for measurement.

4.5.7 Patient-Reported, Observer-Reported, and Clinician-Reported Outcomes

Patients 4 years or older, along with their parent/guardian and nurse/site staff member, will assess pain from the ESA injection and the Mircera injection. Patients who receive an ESA injection during either or both of the screening visits will assess injection pain. Assessments of the Mircera injection will occur at Week 1 (Visit 3) and Week 9 (Visit 6).

Patient-Reported Injection Pain

Patients 4 years old or older will be asked to assess their pain from the injection 5 minutes after the injection takes place. Pain will be rated on a visual analogue scale (VAS) consisting of a 10-cm horizontal line ranging from "did not hurt at all" to "as painful as it could be," as in Schmitt et al. (2006). Scores out of 10 will be determined by measuring the mark on the line. For young children (≥ 4 years old and < 10 years old), five cartoon faces ranging from "neutral" to "very distressed" will be added as a guide. Children under the age of 4 will not be asked to rate their own pain, as reliability is questionable in very young patients.

Parent-Reported Injection Pain

Parents or guardians will be asked to rate observed pain. Pain will be rated on a VAS consisting of a 10-cm horizontal line ranging from "did not hurt at all" to "as painful as it could be." Scores out of 10 will be determined by measuring the position of the mark on the line. As much as possible, the same parent/guardian should rate pain at every visit.

Nurse-Reported Injection Pain

The nurse or site staff member administering the ESA or Mircera doses will be asked to rate observed pain. Pain will be rated on a VAS consisting of a 10-cm horizontal line ranging from "did not hurt at all" to "as painful as it could be." Scores out of 10 will be determined by measuring the position of the mark on the line. As much as possible, the same nurse/site staff member will rate each patient across all visits.

4.6 TREATMENT, PATIENT, STUDY, AND SITE DISCONTINUATION

4.6.1 Study Treatment Discontinuation

Patients must permanently discontinue study treatment if they experience any of the following:

- Any medical condition that the investigator or Sponsor determines may jeopardize the patient's safety if he or she continues to receive study treatment
- Investigator or Sponsor determines it is in the best interest of the patient
- Pregnancy
- Kidney transplantation
- AEAB-mediated PRCA

The primary reason for study treatment discontinuation should be documented on the appropriate eCRF.

In this study, if a patient discontinues study treatment for the reasons mentioned above, he or she will be discontinued from the study. See Section [4.6.2](#) for additional possible reasons for patient discontinuation from study.

4.6.2 Patient Discontinuation from Study

Patients have the right to voluntarily withdraw from the study at any time for any reason. In addition, the investigator has the right to withdraw a patient from the study at any time. Reasons for withdrawal from the study may include, but are not limited to, the following:

- Patient withdrawal of consent
- Study termination or site closure
- Patient non-compliance, defined as failure to comply with protocol requirements as determined by the investigator or Sponsor

Every effort should be made to obtain information on patients who withdraw from the study. The primary reason for withdrawal from the study should be documented on the appropriate eCRF.

In case of premature withdrawal, patients will return to the clinic for a follow-up visit (all assessments for Visit 10, see [Appendix 1](#) for details). In case of premature withdrawal due to a kidney transplantation, the follow-up visit must take place before the transplantation; otherwise, there will be no follow-up visit.

The primary reason for withdrawal from the study should be documented on the appropriate eCRF page. If a patient requests to be withdrawn from the study, this request must be documented in the source documents and signed by the investigator.

Additional patients may be enrolled to replace patients who withdraw early, before the Week 17 (Visit 8).

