5.3.1 Adverse Event Reporting Period

Investigators will seek information on adverse events at each patient contact. All adverse events, whether reported by the patient or noted by study personnel, will be recorded in the patient's medical record and on the Adverse Event eCRF.

After informed consent has been obtained but prior to initiation of study drug, only serious adverse events caused by a protocol-mandated intervention (e.g., invasive procedures such as blood sampling, discontinuation of medications) should be reported (see Section 5.4.2 for instructions for reporting serious adverse events).

After initiation of study drug, all adverse events will be reported until 28 days after the final dose of study drug.

Instructions for reporting adverse events that occur after the adverse event reporting period are provided in Section 5.6.

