5.3.5.10 Loss of Effect

Hb values will be monitored regularly throughout the study, and dose adjustments to achieve target Hb will be made according to protocol guidance (see Section [4.3.2.1.1](#)).

Loss of effect is defined as follows: a decline in Hb of at least 2.8 g/dL in a 4-week period without transfusion or requirement for transfusion of 1 blood unit or more per week for a minimum of 2 consecutive weeks in the absence of overt bleeding or blood loss, under uninterrupted treatment with study drug and with dose changes according to protocol guidance (Eckardt and Casadevall 2003). If loss of effect is suspected, the cause should be actively sought. Possible causes include the following: iron deficiency, infection, inflammation, occult blood loss, hyperparathyroidism, myelofibrosis, and malignancy. If a cause for loss of effect is not found, a hematologist should be consulted (possible bone marrow examination), and an unscheduled blood sample should be obtained for a reticulocyte count and an anti-EPO and anti-Mircera antibody determination. An additional blood sample should also be stored for an anti-PEG antibody determination after the assay has been developed.

If a diagnosis of PRCA is not confirmed, the patient should be maintained on the IMP, and other possible causes of loss of effect should be investigated.

If a diagnosis of PRCA is confirmed, treatment with the IMP should be stopped. The patient should not receive another epoetin, and causes of PRCA should be investigated. Reticulocyte counts and anti-EPO, anti-Mircera, and anti-PEG antibody testing will be performed every 8 weeks until the end of the study (see [Appendix 4](#) for further, detailed guidance).

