#### **4.4.2 Adverse Events**

All AEs recorded in the CRF will be listed and classified by System Organ Class (SOC) and Preferred Term (PT). Events will be coded using the latest version of Medical Dictionary for Regulatory Activities (MedDRA). Adverse event severity will be graded according to the WHO Toxicity Grading Scale for determining the severity of adverse events (refer to Appendix 7 of the study protocol for details). AEs that occurred during the treatment period: from the first treatment dose until 28 days after last dose or until the final visit (whichever is latest) will be summarized. Standard safety analyses for all AEs, related AEs, serious AEs, fatal AEs and AEs leading to study drug modification or discontinuation or withdrawal from study will be performed in terms of frequency tables by event and patient.

All adverse events of special interest (AESI) will be presented. AESI include but are not limited to the following:

- Cases of potential drug-induced liver injury that include an elevated ALT or AST in combination with either an elevated bilirubin or clinical jaundice, as defined by Hy's Law (see Section 5.3.5.7 of study protocol)
- Suspected transmission of an infectious agent by the study drug, as defined below:

Any organism, virus, or infectious particle (e.g., prion protein transmitting transmissible spongiform encephalopathy), pathogenic or non-pathogenic, is considered an infectious agent. A transmission of an infectious agent may be suspected from clinical symptoms or laboratory findings that indicate an infection in a patient exposed to a medicinal product. This term applies only when a contamination of the study drug is suspected.

Adverse events related to covid-19 will be identified using the special covid-19 SMQ containing a narrow basket of preferred terms (PTs) to provide a more targeted list of events related to the SARS-CoV-2 virus. Only events occurring in the pandemic timeframe (1 Dec 2019 onwards) will be included in this list. A listing of such adverse events associated with covid-19 will be provided. For those patients with confirmed covid-19 infection or positive PCR test (9 preferred terms from the above SMQ) any other AEs occurring within  $\leq 7$  days before and  $\leq 30$  days after start date of the AE will also be considered as covid-19 associated events.

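### For early leavers no scheduled contact closes the 28-day adverse event window, transplant patients may have no follow-up visit, and the PRCA discontinuation rule conflicts with 8-weekly testing

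*Protocol*

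**What the plan says.** **Reporting window.** Protocol 5.3.1 states: "After initiation of study drug, all adverse events will be reported until 28 days after the final dose of study drug". Section 5.4.2.2 sets the same limit for serious adverse events and events of special interest. Under 5.3.1, investigators ask about adverse events whenever they are in contact with the patient. SAP 4.4.2 says that events "from the first treatment dose until 28 days after last dose or until the final visit (whichever is latest) will be summarized".

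**Early withdrawal.** Protocol 4.6.2 gives the general rule: "In case of premature withdrawal, patients will return to the clinic for a follow-up visit", with all Visit 10 assessments. Section 4.5 allows that visit "at any time during the study in case of premature withdrawal". Neither section ties it to the date of the last dose. For kidney transplantation, both sections say that "the follow-up visit must take place before the transplantation; otherwise, there will be no follow-up visit".

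**PRCA.** Protocol 4.6.1 lists kidney transplantation and antibody-mediated PRCA among the reasons for permanently stopping treatment, and adds that "if a patient discontinues study treatment for the reasons mentioned above, he or she will be discontinued from the study". Section 5.3.5.10 says that, once PRCA is confirmed and treatment has stopped, reticulocyte counts and "antibody testing will be performed every 8 weeks until the end of the study". Section 3.2 defines the end of the study as the last visit of the last patient.

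**Schedules.** Appendices 1 and 2 contain no contact at day 28 after the last dose for early leavers, and no visits for PRCA follow-up.

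**The concern.** A reporting window works only if someone asks about events up to its end. Completers are asked, because their final visit falls nominally 28 days after the last dose. For a patient who leaves early, the one required visit may come soon after the last dose. A transplant patient may not have even that visit. Events that begin later in the window would then come to light only through an unscheduled contact.

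Safety is a named objective and the study is small, so a few missed events could change the adverse event tables. Patients who stop for a medical reason or a transplant are also those in whom a new event is of particular interest. Nothing in SAP 4.4.2 would tell a reader how many windows were only partly observed.

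The PRCA question is separate. One section takes the patient out of the study and another expects repeated sampling to the end of the study. A site needs to know which applies and under what visit structure.

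**Working it through.** **The plan's withdrawal figure.** Protocol 6.1 and SAP 2.3 assume 30% withdrawal from 40 patients.
- Withdrawals: 0.30 × 40 = 12.
- Remaining: 40 − 12 = 28, which agrees with the plan's statement that more than 26 will have evaluation-period data.
- Twelve is therefore the expected number under the early-withdrawal rule in the core study. No withdrawal rate is given for the extension.
- The precision statement in the same section is not in dispute. With n = 26, SD 1.5 g/dL and no true change, the probability that the 90% CI lies within ±1 g/dL is 92.1% by the normal approximation and 90.4% by simulation with the t quantile. Nothing in this point changes it.

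**Completers.** Inputs are the visit weeks and the ±3-day window in Appendices 1 and 2.
- Core: Week 17 dose to Week 21 visit = 4 × 7 = 28 days.
- Extension: Week 41 dose to Week 45 visit = 28 days.
- If both visits use the ±3-day window, the interval runs from 28 − 6 = 22 to 28 + 6 = 34 days.

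The final visit therefore closes the window nominally.

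**Early leavers.** If the last contact is k days after the last dose, the days with no scheduled contact number 28 − k.

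| Last contact, days after last dose | Days of the window left |
|---|---|
| 0 | 28 |
| 1 | 27 |
| 7 | 21 |
| 14 | 14 |
| 21 | 7 |
| 28 | 0 |

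The value of k depends on circumstances:
- After the Week 1 and Week 17 doses, a visit is scheduled two weeks later (Weeks 3 and 19).
- After the Week 5, 9 and 13 doses, the next scheduled visit is four weeks later. One PK sample, 24 hours to 5 days after any one dose, may add a contact but need not fall in the relevant interval.
- A patient who leaves at the next dosing visit, before being dosed, has k = 28 and a nominally complete window.

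**Transplantation.** Take a patient dosed at Week 13 and transplanted 10 days later. If a follow-up visit is held the day before, k = 9 and 28 − 9 = 19 days remain. If it cannot be arranged, the rule drops it. The dosing visit is then the last scheduled contact, and all 28 days remain. In either case no day after the transplant has a scheduled contact.

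**PRCA.** The number of 8-weekly tests due by Week T after stopping at Week w is the whole part of (T − w)/8.

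| Treatment stops at week | Due by Week 45 |
|---|---|
| 5 | 40/8 = 5 |
| 9 | 36/8 = 4.5, so 4 |
| 13 | 32/8 = 4 |
| 17 | 28/8 = 3.5, so 3 |

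Week 45 is only a convenient horizon. Read literally, the end of the study is the last patient's last visit. For the first patient enrolled, 41 months is about 178 weeks from the start of screening. Taking off 3 weeks of screening and the stopping week, and dividing by 8, gives about 19 to 21 tests. The plan schedules one follow-up visit for such a patient.

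**The case against.** The case on the other side has weight.

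**Other duties exist.** Protocol 4.6.2 says: "Every effort should be made to obtain information on patients who withdraw from the study". Section 5.5.1 has each known event followed until it resolves or is stable, unless the patient is lost to follow-up or withdraws consent. Section 5.5.2 lets the sponsor follow up serious events by telephone, and 5.6 covers related serious events after day 28 if the investigator hears of them. The 28-day duty is itself not limited to scheduled visits. So an event that caused the withdrawal is already followed. What these duties lack is a date or a type of contact that would bring a new event to light.

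**A reader might infer that early leavers go at once, with no further contact.** The text does not say so. Everyone who withdraws early is required to return for a visit, and only transplantation has an exception.

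**A reader might take 12 as the number with an open window.** It is all assumed withdrawals, and some will have a complete window. The rate comes from NH19707, an IV study in hemodialysis patients. The short-notice transplant after Week 13 is a worst case. Planned living-donor transplants within 5 months are given as an example of grounds for exclusion.

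**A reader might infer that adverse event rates are biased by a known amount.** SAP 4.4.2 uses the window to select events and tabulates them by event and patient. It specifies no person-time denominator. Under-capture is possible, but its size cannot be estimated from the documents.

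**A reader might use the half-life of about 130 hours in Protocol 1.2 to calculate drug remaining at the last contact.** That is a single-dose subcutaneous value, and a simple decay from the time of injection ignores absorption. It does not support such percentages here.

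**A reader might conclude that PRCA follow-up is cancelled.** Section 5.3.5.10 can be read as a specific rule that prevails over the general sentence in 4.6.1, and the withdrawal visit and event follow-up still apply. For pregnancy, another listed reason, 5.4.3.1 expressly continues monitoring to the outcome. Section 5.1.1.2 reports no cases in Mircera trials. The two sections still do not say how they fit together, and no visits are provided.

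**Conclusion.** The point holds in limited form. No scheduled contact ensures that adverse events are collected to day 28 after the last dose for early leavers. After a transplant none is scheduled, and a transplant patient may have no follow-up visit at all. New events late in the window may therefore be missed. Up to about 12 of 40 patients come under the rule, if the 30% assumption carries over from NH19707. How many would have an open window, and how many would leave for a transplant, is not stated. Nothing here establishes the direction or size of any bias in the reported frequencies beyond possible under-capture.

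On PRCA, 4.6.1 and 5.3.5.10 conflict as written and must be reconciled. Because the event is very rare, this concerns the clarity of the rule and not an expected count.

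The change is worth making because it is cheap and the gap is in data that the plan itself requires. No sample size, power or efficacy result is affected.

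**What to change.** 1. In Protocol 4.5, 4.6.2 and Appendices 1 and 2, add one adverse event contact at 28 days after the last Mircera dose for every premature withdrawal, including withdrawal for transplantation. A telephone call is enough. Exempt patients for whom consent to contact has been withdrawn, and those whose withdrawal visit already falls on or after day 28.
2. Reconcile 4.6.1 with 5.3.5.10 on follow-up after confirmed PRCA, and make the schedules agree with the result. How to resolve it is for the sponsor to decide.
3. In SAP 4.4.2, report the number of patients whose 28-day window was not fully observed. Counted over all dosed patients, this would also show completers whose final visit fell a few days early.

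The cost is at most about 12 calls in the core study at the assumed withdrawal rate, plus any for extension withdrawals. Beyond that it is a few sentences in the protocol, one count in the SAP and a small amount of site effort.
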